7.1 Nivolumab drug information

| Furthermore, the job title of the coordinating physician noted on |
|---|
| the box will be the title at the start of the trial. If the title changes |
| during the trial, there will be no modification made to the labeling |
| on the box. |

Nivolumab will be provided free of charge by Ono Pharmaceutical who are the investigational drug sponsor. Records of the drug manufacturing and quality testing will also be provided by the sponsor.

| Investigational drug | Regorafenib |
|-----------------------|---|
| Formulation: | Light red elliptical film coated tablet |
| Manufacturer: | Bayer Yakuhin, Ltd |
| Content: | Hard capsule containing 40 mg of regorafenib |
| Usage: | Given once daily for the first 21 days of each 28 day cycle. |
| Administration route: | Oral |
| Expiration date | Refer to the procedures regarding investigational drug management |
| Labeling | The outside of the box lists the investigational drug code name, content, lot number, expiration date, number of doses, and storage method along with the name, job title and address of the coordinating physician. The box will also note that the drug is for use in the trial. Furthermore, the job title of the coordinating physician noted on the box will be the title at the start of the trial, and if the title changes during the trial, there will be no modification made to the labeling on the box. |
| Storage method | Store at 2°C–8°C in an airtight container away from light. |

7.2 Regorafenib drug information

Regorafenib will be provided free of charge by Bayer Yakuhin, Ltd who are the investigational drug sponsor. Records of the drug manufacturing and quality testing will also be provided by the sponsor.

7.3 Investigational drug management

After the investigational drugs (i.e., regorafenib and nivolumab) have been transported to the pharmacy at the National Cancer Center Hospital East from Bayer and Ono Pharmaceuticals, the drugs will be stored by the said pharmacy.

The investigational drug manager at each participating medical institution will receive, handle, manage, store, and dispense the investigational drugs in accordance with the procedures regarding investigational drug management provided by the principal investigator. The investigational drug manager will also return or dispose of nondispensed drugs and unused drugs that have been collected from subjects in an appropriate manner. Records of such procedures are to be created and maintained

on file.

Furthermore, the attending physician will prescribe the number of doses of the investigational drug considered valid according to this trial protocol, and collect any unused investigational drugs recovered from the subjects. The collected unused drugs will then be returned to the investigational drug manager.

Moreover, the investigational drugs are not to be administered by any method other than that stipulated in this trial protocol.

Throughout the study, all unused study medication will be accounted for. The information will be recorded in the drug dispensing log.

7.4 Anticipated adverse events

Regarding any anticipated adverse events caused by regorafenib and nivolumab, with reference to the latest investigator's brochure, adverse events for which the onset tendency (including the onset or the number of occurrences, incidence, and onset conditions) of the adverse event concerned cannot be foreseen according to the investigator's brochure of the investigational drug concerned shall be referred to as "unknown," whereas those that can be foreseen shall be "known."

8 Endpoints, laboratory tests, and evaluation schedule

8.1 Observations, tests, and endpoints

Table 8.1: Observations, tests, and endpoints

| Item | Details |
|--------------------|--|
| Dosing situation | The regorafenib and nivolumab dose, treatment start date, treatment |
| | completion date or treatment termination date (dose withholding date), |
| | presence or absence of dose changes and associated reasons, presence or |
| | absence of dose withholding, number of times doses are withheld and |
| | associated reasons. |
| Subject background | Medical record number or identification number (number with which the |
| | patient can be identified). |
| | Sex, age, main medical history/complications/drug allergies, type of cancer, |
| | histology (e.g., pap, tub1, tub2, por1, por2, sig, muc, or other), HER2 |
| | (negative, positive, or unknown), EBV (negative, positive, or unknown), |
| | presence or absence of RAS mutation (when known), MSI status (when |
| | known), lesion site (primary site, target lesion, or nontarget lesion) and |
| | history of prior treatment (chemotherapy, radiotherapy). |
| Physical | Height and weight |
| measurements | |
| Vital signs | Body temperature, heart rate, and systolic/diastolic blood pressure |
| General condition | PS (ECOG) |
| Adverse events | ≥Grade 1 subjective and objective symptoms |
| Concomitant | Drug name, administration route, administration start date, administration |
| drugs/combination | completion date, reason for combination therapy |
| therapy | |
| Blood testing | White blood cell count, neutrophil count, red blood cell count, hemoglobin, |
| | hematocrit, and platelets |
| Biochemistry | AST (GOT), ALT (GPT), ALP, LDH, albumin, total bilirubin, direct |
| | bilirubin, BUN, creatinine, CK, lipase, electrolytes (Na, K, Cl, Ca, IP and |
| | Mg), UA, and blood glucose (fasting and intermittent) |
| Blood coagulation | PT, INR, and APTT |
| test | |
| Urine analysis | Urinary protein, urinary sugar, and occult blood in urine |
| Thyroid function | Thyroid stimulating hormone, free triiodothyronine (fT3), and free |
| | thyroxine (fT4) |

| Pregnancy test | When pregnancy is suspected on the basis of urine analysis, blood testing |
|---------------------|---|
| | shall be performed. |
| | Tests shall be performed in premenopausal women and women who |
| | experienced their last menstruation <1 year ago. |
| Tumor markers | |
| | Stomach cancer/colorectal cancer: CEA, CA19-9, Hepatocellular |
| | carcinoma : PIVKA-II, and alfa-fetoprotein (AFP) |
| Electrocardiography | 12-lead electrocardiography (ECG) at rest |
| Infection | HIV antibody, HBs antigen, HBs antibody, HBc antibody, HCV antibody |
| | and HBV-DNA assay |
| Tumor evaluation | Chest/pelvic contrast-enhanced CT*, or abdominal/pelvic contrast-enhanced |
| | MRI*, as well as chest X-ray, brain CT, and brain MRI as required |
| | *In subjects with allergies/hypersensitivities to the contrast medium used |
| | for CT and MRI, the tests can be performed without a contrast medium. |
| | When treatment is terminated for reasons other than an exacerbation of the |
| | underlying disease on imaging, evaluations shall be performed until an |
| | exacerbation is confirmed. |
| Outcome | The presence or absence of aftertreatment shall be investigated, and in the |
| investigation | event that aftertreatment is administered, the treatment method and the start |
| | date shall be recorded. |
| | The date of death, or last day of confirmed survival, and in the event of |
| | death, the cause of death shall be investigated. |
| | *Even if a subject cannot be directly followed up for reasons such as |
| | hospital transfer, survival is to be confirmed as far as possible by contacting |
| | the hospital where the subject was transferred, and the result of such contact |
| | is to be noted in the medical records. |
| | |

8.2 Observation and test schedule

The observation and testing schedule is presented in Table 9. When the principal investigator (or subinvestigator) deems it necessary to perform additional tests or observations, they will be performed in addition to the schedule presented in Table 9.

Table 8.2 Schedule

| Cycle | Screening | Investigational drug administration period | Terminat | 30 days | Follo |
|-------|-----------|--|----------|---------|-------|
|-------|-----------|--|----------|---------|-------|

| | period (-14 days to day 0) | | Су | cle 1 | | Cycl | le 2 ards | ion date ^{d)} | after last dose ^{e)} | w-up perio d |
|--|----------------------------------|-----------------|---------------|---------------|---------------|---------------|---------------|---------------------------|----------------------------------|--------------------|
| Day Permissible rang | je | 1 | 8 | 15 | 22 | 1 | 15 | Day 0 to +7 | Day -3 to +7 | |
| Visit | | 0 | 0 | 0 | 0 | 0 | 0 | 0 | 0 | 0 |
| Treatment | | | | | | | | | |   |
| Regorafenib treatment | | \rightarrow | \rightarrow | \rightarrow | | \rightarrow | \rightarrow | | | |
| Compliance | | 0 | | | | 0 | | | | |
| Nivolumab treatment | | 0 | | 0 | | 0 | 0 | | | |
| Background, etc. | 1 | | | 1 | | | 1 | | | 1 |
| Consent acquisition | 0 | | | | | | | | | |
| Verification of inclusion criteria and exclusion criteria | 0 | | | | | | | | | |
| Subject background | 0 | | | | | | | | | |
| Body meas | 0 | | | | | | | | | |
| urem Weight ents | 0 | ₀ c) | | | | 0 | | 0 | 0 | |
| vital signs/PS Weekly BP monitoring for the first 6 weeks | 0 | 0 | 0 | 0 | 0 | 0 | 0 | 0 | 0 | |
| Combination drugs/therapies with adverse events | 0 | 0 | \rightarrow | \rightarrow | \rightarrow | \rightarrow | \rightarrow | \rightarrow | → | |
| Laboratory tests | | 1 | | | | | | 1 | | |
| Blood tests (blood count, biochemistry ^{g)}) | 0 | ₀ c) | 0 | 0 | 0 | 0 | 0 | 0 | 0 | |
| Urine analysis | 0 | ₀ c) | 0 | 0 | 0 | 0 | 0 | 0 | 0 | |

| Thyroid function | 0 | ₀ c) | | | | 0 | | 0 | | |
|------------------------------|-----------------|---|-------|---|--|---|--|---|---|---|
| Coagulation test | 0 | ₀ c) | | | | 0 | | 0 | | |
| Pregnancy test ^{a)} | 0 | | | | | | | | | |
| Tumor markers | 0 | ₍₎ c) | | | | 0 | | 0 | | |
| 12-lead ECG | 0 | ₍₎ c) | | | | 0 | | 0 | | |
| Infection test | _O b) | | | | | | | | | |
| Tumor evaluation | • | | | • | | | | | | |

- g) Only subjects who received explanation from the doctor agree to perform before and after protocol treatment start 4-6 weeks, at the time of discontinuation. Refer to 8.6

8.3 Examination findings

8.3.1 Subject background

Clinical diagnosis

Primary and metastatic lesion sites, etc.

• The following details will be collected regarding the time of the initial histological diagnosis (month and year), histological diagnosis, and the presence or absence of pretreatment.

surgery

• chemotherapy(Number of enforcement regimens, pretreatment anti-PD1 / PD-L1 administration)

radiation

other treatments

8.3.2 Height and weight measurements and vital signs

The subject's vital signs (i.e., blood pressure, heart rate, and body temperature) as well as body height/weight will be measured. Vital signs are to be measured at each examination with the subject in the same position each time.

8.3.3 ECOG performance status (PS)

The ECOG PS will be measured (refer to appendix 1).

8.3.4 Adverse events (subjective and objective symptoms)/combination therapy

During the period from the start of treatment until 30 days after completion of the treatment protocol, adverse events (subjective and objective symptoms) are to be monitored and recorded. Refer to section 11 on the reporting of adverse events for details regarding the handling of adverse events.

8.4 Laboratory tests

The test items listed in Table 8.1 are to be measured in accordance with the time indicated in the schedule presented in Table 8.2.

8.4.1 Blood tests/biochemical tests/blood coagulation tests/urine analysis/hormone analysis

/thyroid function tests

The items listed in Table 8.1 will be tested in accordance with the time indicated in the schedule presented in Table 8.2, and when deemed clinically necessary. If needed, the evaluation of clinically significant laboratory tests will be repeated until the test values return to baseline values, until clinically stable, or until a different treatment is initiated. And appropriate test items for adrenocorticotropic hormones (such as ACTH) will be added as needed.

8.4.2 Tumor markers

The items listed in Table 8.1 are to be measured in accordance with the time indicated in the schedule presented in Table 8.2.

8.4.3 Pregnancy tests

In the case of a female subject capable of childbearing, confirmation that the subject is not pregnant will be obtained by urine test <7 days before enrollment in the trial. If pregnancy is suspected in the urine test, the pregnancy will be determined by a blood test. Female subjects deemed incapable of childbearing include those who have experienced menopause (the absence of menstrual periods for >1 year), and those who have undergone tube ligation or hysterectomy, the details of which are to be noted in the source document of the subject.

8.4.4 Infection tests

HIV antibody, HBs antigen, HBs antibody, HBc antibody, HCV antibody and HBV-DNA assay are to be measured before enrollment. Furthermore, in the event that results are available for tests conducted <12 months before enrollment, these results may be used instead.

(HBV-DNA assay are measured only when either HBs antibody or HBc antibody are positive.

8.4.5 Twelve-lead ECG at rest

For the 12-lead ECG, data recording will be initiated after confirming that the subject is resting in the dorsal position. A physician suited to the ECG evaluation will evaluate the QT interval, as well as qualitative abnormalities in the ST segment form, the T-wave form, and the presence or absence of a U-wave.

8.5 Tumor evaluation

For all subjects, tumor evaluations will be conducted using the irRECIST and RECIST guidelines version 1.1. Tumor evaluations of the chest, abdomen, and pelvis (when deemed clinically necessary) will be conducted at each time point listed below until an exacerbation is

confirmed. Thoracoabdominal and pelvic contrast-enhanced CT or MRI will be performed (if the subject is allergic to the contrast medium, plain scans are permitted).

- Less than 21 days before enrollment in this trial
 - Evaluations will be performed in weeks 6, 12, 18, and 24 after the beginning of treatment (followed by every 9 weeks until week 42, then every 12 weeks thereafter).
- When treatment is terminated for reasons other than an exacerbation of the underlying disease on imaging, an evaluation will be performed within 2 weeks of dosing completion. Furthermore, tumor evaluations are to be conducted in accordance with the schedule until an exacerbation of the underlying disease is confirmed, or until commencement of a new anticancer treatment.

The principal investigator and radiologist will conduct tumor evaluations in accordance with the irRECIST and RECIST guidelines version 1.1 (refer to appendices 2 and 3). The decision to continue the investigational drugs will be determined on the basis of these evaluations, including the effects on target and nontarget lesions and the appearance of new lesions. When disease progression is first observed on imaging in clinically stable patients, participating medical institutions will conduct repeat scans 4 weeks after the initial identification of disease progression via an image evaluation to determine disease progression. Administration of the investigational drug can continue until the repeat scan is conducted (refer to Table 10). The criteria for clinical stability are listed below.

- Absence of clinical signs and symptoms indicating disease progression.
- No worsening of ECOG PS.
- No sudden disease progression observed

• Absence of tumor enlargement in the main anatomical site requiring new emergency medical intervention (e.g., spinal cord compression).

Furthermore, in the present trial, a maximum of 10 lesions can be included as target lesions, with a maximum of five lesions per organ.

| Table 8.5: Imaging and investigational drug dosing after disease progression is first observed |
|--|
| on imaging |

| | Clinically stable | | | | Clinically unstable | | | |
|----------------------|-------------------|--|--------------------|-----------------|---------------------|--------|-----------------|--|
| | Imaging | | Investigational | Imaging | | | Investigational | |
| | | | drug dosing | | | | drug dosing | |
| Disease | To confirm | | Investigational | If | poss | sible, | Interruption of | |
| progression is first | disease | | drug dosing can be | repeat the test | | dosing | | |

| determined by | progression, | continued at the | after 4 weeks to | |
|------------------|-----------------|---------------------|------------------|-----------------|
| imaging | repeat the test | discretion of the | confirm disease | |
| | after 4 weeks | attending | progression | |
| | | physician until | | |
| | | disease | | |
| | | progression is | | |
| | | confirmed by | | |
| | | retesting at the | | |
| | | participating | | |
| | | medical institution | | |
| | | | | |
| Disease | Additional | Terminate dosing | Additional | Not applicable |
| progression is | imaging is not | of the | imaging is not | |
| determined by | necessary | investigational | necessary | |
| repeat imaging | | drug (exceptions | | |
| | | can be permitted | | |
| | | upon deliberation | | |
| | | with the trial | | |
| | | coordinating | | |
| | | committee) | | |
| SD, PR, or SD is | Continue the | Continue the | Continue the | When the |
| determined by | prescribed | investigational | prescribed | subject's |
| repeat imaging | routine imaging | drug at the | routine imaging | condition |
| | every 6 weeks | discretion of the | every 6 weeks | improves, or |
| | | attending | | when the |
| | | physician | | subject is |
| | | | | clinically |
| | | | | stable, dosing |
| | | | | of the |
| | | | | investigational |
| | | | | drug can |
| | | | | resume at the |
| | | | | discretion of |
| | | | | the attending |
| | | | | physician |

In the event of clear clinical progression according to symptom exacerbation as judged by the attending physician, treatment should be terminated even if there is no confirmed progression according to an image diagnosis. Symptoms indicating clinical progression must be recorded in the subject's medical records. Efforts shall be made to confirm progression objectively by imaging as much as possible, even after termination of treatment.

8.6 Biomarker Biopsy Blood sampling

Before and after the start of the investigational medicine, serum (or plasma), immunocompetent cells such as mononuclear cells, residual diseased tissue are obtained from peripheral blood and lesion tissue (biopsy specimen) around 4-6 weeks after start. For subjects who had a therapeutic effect, blood specimens and tissue specimens may be obtained after disease progression only when consent is obtained from subjects (for details see the accompanying research implementation plan).

8.7 Follow-up

Outcome investigations will be performed after termination of the treatment protocol until the subject dies, or up to 2 years after the day that the last subject enrolled in the present trial. Even when direct follow-up is not possible (e.g., because of hospital transfer), the hospital where the subject was transferred will be contacted to verify the outcomes as far as possible. The results of such contact are to be noted in the subject's source documents.

9 DATE COLLECTION

9.1 Handling and Retention of CRF Data

Data will be managed, and CRF data will be managed and retained by the Data Management Office, Clinical Research Support Unit, National Cancer Center Hospital East. A data management plan will be prepared. In the plan, access restriction such as inputting in and browsing the database will be set, and records will be properly controlled and kept.

9.2 Identification of Source Documents

Source documents in this study will be as follows: Medical records Informed consent form Investigational drug management table Laboratory test data Diagnostic imaging films, etc.

10 Reporting of adverse events

10.1 Adverse event evaluation

10.1.1 Definition of adverse events

Adverse events include all undesirable or unintentional signs, symptoms, and conditions (including abnormal changes in laboratory test values) that arise in subjects administered the investigational drugs, regardless of the presence or absence of a causal relationship with the investigational drug concerned.

When \geq grade 1 subjective or objective symptoms are observed before the start of treatment (at the time of the baseline evaluation), only those for which the grade of the adverse event concerned deteriorates compared with the pretreatment level will be treated as adverse events.

10.1.2 Method of recording adverse events

When signs (including abnormal laboratory test values) and symptoms are included in the diagnosis, the name of the diagnosis according to the CTCAE will be recorded on the CRF as far as possible, rather than each individual sign and symptom.

Abnormalities in laboratory test values will be reported as adverse events only when the attending physician deems that any of the following conditions are satisfied:

- 1) When clinical signs or symptoms are induced
- 2) When deemed clinically important
- 3) When treatment is required
- 4) When additional tests are required (only repeat tests are exempt)
- 5) When termination or dose reduction of the investigational drug is required

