6.1.3 Definition of DLT

As a general rule, DLT includes the observation of any of the side effects listed below during the DLT evaluation period and will ultimately be determined upon deliberation between the sponsor and the principal investigator of the trial. Furthermore, the opinion of the Data and Safety Monitoring Committee can be sought as required (refer to attachment 1: trial protocol [supplement]).

• Hematotoxicity:

–Persistent grade 4 neutropenia lasting \geq 7 days;

-When a neutrophil count of <1000/mm³ and fever of $\ge 38.0^{\circ}$ C is observed for >2 days;

-Grader 4 thrombopenia or thrombopenia associated with a hemorrhage requiring platelet transfusion.

- Grade 3 thrombocytopenia with bleeding.

• Non-hematotoxicity:

 \geq Grade 3 non-hematotoxicities. However, any of the following non-hematotoxicities will be deemed DLT when it is judged by the principal investigator or subinvestigator that treatment cannot be continued even with supportive therapy.

- \Rightarrow 2Grade 3 diarrhea, nausea, vomiting, and loss of appetite for \geq 5 consecutive days;
- \Rightarrow 2Grade 3 electrolyte imbalance for 27 consecutive days;
- \Rightarrow \geq Grade 3 dermal toxicity for \geq 7 consecutive days;
- ♦ Grade 3 or more immune related adverse event that lasts more than 8 days even after steroid therapy is applied.

• General:

When 70% of the planned regorafenib dose cannot be administered, and/or when one dose of nivolumab cannot be administered because of toxicity during the DLT evaluation period

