6.3.1.4 Resumption of regorafenib dosing

When regorafenib is administered, if you develop diarrhea, fatigue, loss of appetite, nausea, vomiting, and other adverse events judged by your doctor as Regorafenib (excluding asymptomatic test values) that cannot deny the causal relationship with Regorafenib, "Table 6.3.1.4 Dose Adjustment for Other Adverse Events ", the investigational physician judges and adjusts the dose.

| NCI CTCAE Grade | Possibility to continue | Dose adjustment | | | |
|-----------------|-------------------------------|------------------|--|--|--|
| | administration | | | | |
| Grade 2 | Continue administration | No change | | | |
| Grade 3 | Weigh out until recovering to | Reduce one level | | | |
| | Grade 2 or lower | | | | |
| Grade 4 | Discontinue administration | — | | | |

Table 6.3.1.4 Dose Adjustment for Other Adverse Events

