12.12.2 Analysis items included in the clinical study report

The following analysis items will be included in the clinical study report.

<Efficacy evaluation (Analysis population: all enrolled patients)>

- Demographic data
- Objective response rate (ORR)
- Disease control rate (DCR)
- Progression-free survival (PFS)
- Overall survival (OS)

<Safety evaluation (Analysis population: SP)>

- Incidences of DLTs/AEs (number of patients with DLTs/AEs and the incidence, by the worst grade)
- Summary statistics of laboratory values and their changes

<Tables, figures and graphs referred to but not included in the text of the clinical study report>

- Listings of deaths, other serious and significant adverse events
- Laboratory value listing by patient

<Appendix>

- List of discontinued patients
- List of patients with serious protocol deviations
- List of patients excluded from FAS
- History of prior treatment
- List of concomitant medications and therapies
- Compliance
- List of efficacy response data by patient (tumor assessment, OS, PFS, subsequent treatment, and tumor markers)
- Adverse event listing by patient

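### Section 10.1.2 lets an asymptomatic grade 3 laboratory value go unreported as an adverse event, so the worst-grade AE table may undercount laboratory toxicity, and no table of laboratory grades is planned

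*Combined protocol and SAP*

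**What the plan says.** - **Definition (10.1.1).** AEs take in undesirable signs, symptoms and conditions, "including abnormal changes in laboratory test values) that arise in subjects administered the investigational drugs". No judgement filter is attached.
- **Reporting (10.1.2).** "Abnormalities in laboratory test values will be reported as adverse events only when the attending physician deems" that at least one of five conditions holds: (1) the abnormality produces signs or symptoms; (2) "When deemed clinically important"; (3) it needs treatment; (4) "When additional tests are required (only repeat tests are exempt"); (5) "When termination or dose reduction of the investigational drug is required".
- **Endpoint and analysis (11.2.1, 12.6.1).** The incidence of each AE is calculated by worst CTCAE v4.03 grade over all cycles. It is summarised in the safety population without confidence intervals.
- **Other laboratory output (12.12.1, 12.12.2).** The study report contains "Summary statistics of laboratory values and their changes", and a per-patient laboratory listing is kept outside its text. Section 12.12.1 names mean, median, minimum and maximum. No tabulation by CTCAE grade is specified.
- **DLT definition (6.1.3).** "Grade 3 non-hematotoxicities" and worse are dose-limiting, with qualified clauses for some toxicities, including electrolytes. Asymptomatic or temporary laboratory values are not mentioned. Section 6.2.1 does exempt temporary test abnormalities from its grade 4 termination rule, and 6.3.1.4 adjusts regorafenib for other AEs "excluding asymptomatic test values".

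**The concern.** The definition and the reporting rule do not cover the same events. What reaches the AE table is set by the attending physician's view of each abnormal value, in an open-label trial whose purpose is safety and dose selection. Two patients with the same recorded grade 3 value can be counted differently. The direction is fixed: 10.1.2 can only remove laboratory abnormalities from the AE table. The planned laboratory output does not restore the count, because means, medians and ranges do not show how many patients reached grade 3. A reader would have to grade the patient listings by hand.

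**Working it through.** The plan gives no laboratory toxicity rate and no reporting rate, so there is no figure of its own to reproduce. The check has two steps.

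**Step 1: can a grade 3 value miss all the objective conditions?**

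*Asymptomatic grade 3 lipase or CK.* Both are scheduled biochemistry tests (Table 8.1).
- Condition 1 is not met, since there are no symptoms.
- Condition 3 is not met if no treatment is given.
- Condition 4 is not met if the value is only repeated.
- Condition 5 is not met through regorafenib, because 6.3.1.4 leaves asymptomatic test values out of its dose adjustment. If the value is attributed to nivolumab, the Table 6 row for other related toxicities at grade 3 starts with withholding, which is not termination or dose reduction.
- Only condition 2 remains, and it is discretionary.

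*First grade 3 AST/ALT rise attributed to regorafenib alone.* Table 5 in 6.3.1.3 has regorafenib withheld and allows it to resume at the same dose, with weekly re-measurement.
- Section 6.1 defines termination as not resuming the drug, so withholding followed by the same dose does not meet condition 5.
- The weekly measurements are repeat tests, so they need not meet condition 4.
- With no symptoms and no treatment, again only condition 2 remains.

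The gap can therefore be reached with the text followed as written.

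**Step 2: how large could it be?** Let N be the number of patients, p the proportion with such a laboratory value, and c the share of those whom the physician reports as having an AE. Both p and c are assumptions.

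- Expected patients by laboratory grade: N × p
- Expected patients in the AE table: N × p × c
- Expected shortfall: N × p × (1 − c)
- Probability that at least one patient is missed: 1 − [1 − p(1 − c)]^N

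N = 30 is the expansion cohort. N = 48 adds the maximum of 18 dose-escalation patients (2.8.2): 18 + 30 = 48.

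| N | p | c | By laboratory grade | In AE table | Shortfall | P(at least 1 missed) |
|---|---|---|---|---|---|---|
| 30 | 10% | 75% | 3.0 | 2.25 | 0.75 | 0.53 |
| 30 | 20% | 50% | 6.0 | 3.0 | 3.0 | 0.96 |
| 30 | 30% | 50% | 9.0 | 4.5 | 4.5 | 0.99 |
| 48 | 10% | 75% | 4.8 | 3.6 | 1.2 | 0.70 |
| 48 | 20% | 50% | 9.6 | 4.8 | 4.8 | 0.99 |
| 48 | 30% | 50% | 14.4 | 7.2 | 7.2 | >0.99 |
| either | any | 100% | N × p | N × p | 0 | 0 |

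Over p = 10–30% and c = 50–100%, the expected shortfall runs from 0 to 4.5 patients of 30, or 0 to 7.2 of 48. A table computed from the recorded values has no shortfall of this kind, by construction.

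**The case against.** The case for leaving the plan alone has four parts.

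1. **Condition 2 is a catch-all.** Most physicians would call a grade 3 value clinically important, above all one judged dose-limiting. That is plausible, and the shortfall is then small or nil. But no sentence requires it, and none says that a DLT must be recorded as an AE.

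2. **Many values meet condition 3 or 5 anyway.** This stands, and it limits the point to asymptomatic grade 3. At grade 4, Table 5 discontinues regorafenib for liver values, most rows of Table 6 terminate nivolumab, and 6.2.1 ends protocol treatment for related grade 4 non-haematological toxicity other than temporary test abnormalities. Grade 3 liver values attributed to nivolumab lead to termination under Table 6, subject to its footnote for liver metastasis and hepatocellular carcinoma, and to corticosteroids under 6.3.2.1.

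3. **Such a value is still an AE.** This is correct. A reader might infer that it is not an AE at all, but 10.1.1 includes it. Section 10.1.2 restricts what is reported.

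4. **DLTs are handled separately.** This also stands. A reader might infer that the DLT count, and so dose escalation, depends on 10.1.2. Nothing in 6.1.3 makes AE reporting a precondition: the sponsor and the principal investigator settle DLT status by deliberation. Section 12.12.2 tabulates DLT incidence as well, so a laboratory DLT would appear in the report even if it was not reported as an AE. Uncertainty over whether an asymptomatic value is a DLT comes from 6.1.3 itself.

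**Conclusion.** The point holds in limited form. An asymptomatic grade 3 laboratory value managed only by observation, repeat testing or withholding can go unreported as an AE, so the worst-grade AE incidence may undercount laboratory toxicity. That it does undercount is not shown. The range of 0 to 4.5 patients of 30 rests entirely on assumed values of p and c.

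The consequence falls on a descriptive secondary safety table. The individual values remain available in the listings. What is missing is a count by grade that does not depend on discretion. Adding it is a cheap improvement; its absence does not threaten the primary endpoint.

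A separate inconsistency remains: 6.2.1 and 6.3.1.4 make exceptions for temporary or asymptomatic test values and 6.1.3 makes none, so sites cannot tell whether the silence in 6.1.3 is intended.

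**What to change.** 1. In 12.6.1 and 12.12.2, add for the safety population a table of the worst post-baseline CTCAE v4.03 grade of each scheduled laboratory test, as a shift from baseline. Compute it from the recorded values regardless of AE reporting, and show it beside the AE incidence. Section 10.1.2 can stay as the rule for what is entered as an AE term.
2. State in 10.1.2 that every laboratory value judged a DLT is also recorded as an AE.
3. Reconcile 6.1.3 with 6.2.1 and 6.3.1.4 on asymptomatic or temporary test values. Which rule applies is for the sponsor to decide.

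Cost: one programmed table from data already collected, which needs each laboratory's normal ranges where grades are multiples of the upper limit, plus two short text changes. Reported laboratory toxicity may look somewhat higher than under the present rule.
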